7.5 Statistical Analysis

We are combining quantitative and qualitative methods of analysis to capitalize on the respective strengths of each of the approaches. The mixed methods will help to evaluate the intervention effect from a patient perspective, as well illustrate the conclusions derived from the quantitative data with stakeholder insight (Bharmal et al., 2018).

The overall design is sequential: QUAN Phase 1 informs QUAN + qual Phase 2, which informs convergent design Phase 3 (QUAL + quan), Itemised methods of analysis are described below:

Content Validity Index (CVI)

To be measured using Lynn's (1986) method:

Experts will rate each item using a four-point ordinal scale (1 = not relevant, 2 = somewhat relevant, 3 = quite relevant, and 4 = highly relevant)

Number of experts rating the item 3 or 4 will be divided by total number of experts
Result of 0.78 or above will be accepted as having met the validity threshold.
Scale content validity ratio will be calculated as a proportion of total items judged against content valid items.

Cognitive interviews

SU Non CTIMP Healthcare Research Protocol

Think aloud technique combined with participant confidence rating (the degree of confidence participant has in their answer) and observation (eg. To find out where people start reading, whether they look for instructions, whether they take longer to answer any particular questions)

Contrast group construct validity

Numerical value will be added to ADRe responses (0 for 'no' answers and 1 for 'yes' or 'worse' answers. Numbers of problems will be compared for the group (n=20) without prescribed medicines and the group (n=20) that is prescribed > 4 medicines (these are participants of 1.2 ADRe testing).

Inter-rater Reliability (IRR)

Cohen's Kappa will be calculated (Cohen, 1960) to compare patient and researcher completion.

Randomised Controlled Trial

Data will be entered into excel via the electronic version of ADRe, imported into SPSS and described for the before and after ADRe administrations. Statistical analysis: differences between before and after the intervention will be calculated for: number and nature of problems addressed, prescription regimens, and NHS use. The impact of GP practice, age, diagnoses, and medicines' use (numbers and types of medicines prescribed) will be described and accounted for in exploratory bivariate and multivariate regression analyses. To explore the recorded changes and potential for further clinical gains, putative aetiologies of service users' signs and symptoms will be ascribed, using clinical information from medical and nursing records, including, but not restricted to, information on ADRe, and the list of medications prescribed (and over the counter). The ascription will be checked by supervisors using manufacturers' literature and formularies. Juxtaposition of ADRe and medication lists will generate suggestions for changes to improve the processes and possibly the outcomes of care. The prevalence of problems on the before and after profiles will be compared with two by two contingency tables, using McNemar's test for related dichotomous variables (Altman 1991).

Survey

Data will be described using the Statistical Package for Social Sciences (SPSS) and later combined with the interview results.

Interviews and recorded ADRe consultations

All interviews (and relevant parts of ADRe consultations) will be transcribed verbatim by the researcher/professional transcriber and anonymised. Transcripts will be

SU Non CTIMP Healthcare Research Protocol

coded, categorised, analysed and interpreted alongside the data of all completed cases, to identify, analyse and report patterns within data (Braun and Clark, 2006). The transcripts will be analysed by the team using the constant comparative method which will provide a systematic, re-iterative way of comparing and contrasting emerging codes, categories and concepts and ensure that theoretical perspectives are embedded in the description of change. Two researchers ([name]) will ensure validity of the analysis and verify interpretation. Disagreements will be resolved through discussion at team meetings. Diaries/logs will also be analysed in association with interview transcripts.

Triangulation

Survey and interview data will be integrated with the outcome measures documented on the ADRe Profile, taking a pragmatic perspective of complementary triangulation (Östlund et al., 2011). Resulting cross-cutting themes derived from the data should enhance understanding and validity, and contextualise the ADRe data (Foss & Ellefsen, 2002; Denzin, 2012).

Costs

Resource use, costs, and health economic outcome measures will be described using the Personal Social Services Research Unit (PSSRU) unit costs of health workers (www.pssru.ac.uk) and the National Tariff Payment Systems.

The regulatory and governance requirements will be met through gaining approval from the relevant review bodies to conduct the project.

8. Data Handling & Record Keeping

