	
outcomes of care. The prevalence of problems on the before and after profiles will be compared with two by two contingency tables, using McNemar's test for related dichotomous variables (Altman 1991).
 
Survey
 
Data will be described using the Statistical Package for Social Sciences (SPSS) and later combined with the interview results.
 
Interviews and recorded ADRe consultations
 
All interviews (and relevant parts of ADRe consultations) will be transcribed verbatim by the researcher/professional transcriber and anonymised. Transcripts will be coded, categorised, analysed and interpreted alongside the data of all completed cases, to identify, analyse and report patterns within data (Braun and Clark, 2006). The transcripts will be analysed by the team using the constant comparative method which will provide a systematic, re-iterative way of comparing and contrasting emerging codes, categories and concepts and ensure that theoretical perspectives are embedded in the description of change. Two researchers ([name]) will ensure validity of the analysis and verify interpretation.
 
Disagreements will be resolved through discussion at team meetings. Diaries/logs will also be analysed in association with interview transcripts.
 
Triangulation
 
Survey and interview data will be integrated with the outcome measures documented on the ADRe Profile, taking a pragmatic perspective of complementary triangulation (Östlund et al., 2011). Resulting cross-cutting themes derived from the data should enhance understanding and validity, and contextualise the ADRe data (Foss & Ellefsen, 2002; Denzin, 2012).
 
Costs
 
Resource use, costs, and health economic outcome measures will be described using the Personal

--	---

SU Non CTIMP Healthcare Research Protocol

	
Social Services Research Unit (PSSRU) unit costs of health workers (www.pssru.ac.uk) and the National Tariff Payment Systems.
 
The regulatory and governance requirements will be met through gaining approval from the relevant review bodies to conduct the project.

--	--

Protocol Agreement Page

The clinical study as detailed within this research protocol

(Version 2, dated 8th January, 2021),

or any subsequent amendments will be conducted in accordance with the

- UK Policy Framework for Health and Social Care Research (2017)
- Medicines for Human Use (Clinical Trials) Regulations (2004)
- Medical Devices Regulations (EU MDR/IVDR 2017)

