2.2 Trial Design

Phase 1

- Validity testing: content validity index (CVI), cognitive interviews, construct validity testing
- Feasibility trial
- Reliability testing (inter-rater reliability)

Phase 2

[figure not shown]
- Randomised controlled trial (cluster group randomization by GP practice, intervention arm (ADRe Profile implementation), control arm (standard of care))

Phase 3

- Interviews and survey with participants of phase 2

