4.3 Randomisation Procedures (if applicable)

Randomisation of participants in Phase 2 will be performed to promote internal design validity and minimise the effects of confounding. To avoid selection bias and enable allocation concealment, GP practices will be selected and patients consented before randomization. While masking is not possible due to the design of the study, ascertainment bias will be lowered by researchers not being aware of the randomization results until after they have accessed the nursing and medical notes and elicited necessary data. Cluster randomization will allow each practice its own care as an independent entity and will minimize contamination. The cluster design has been accounted for in the sample size.

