7.1 Primary Endpoint Efficacy Analysis

Differences between before and after the intervention will be calculated for: problems addressed, prescription regimens, NHS use, and compared, adjusting for site. The impact of age, diagnoses, and medicines' use (numbers and types of medicines prescribed) will be accounted.

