7.4 Sample Size

RCT (sample = 60): Previously, in a 'before and after' single arm intervention study, with participants acting as their own controls, 17/19 (89%) had improvement in at least 1 clinical problem when ADRe Profiles for polypharmacy were used (Jordan et

SU Non CTIMP Healthcare Research Protocol
al submitted). We hypothesised that 9/19 (47%) would have shown some improvement without intervention, necessitating an effective sample of 40 patients (20 in each arm), with 5% significance and 90% power (Uitenbroek 1997). Based on the reported intra-cluster coefficient (0.02), (Jordan et al 2015), and a design effect of 1.18, to achieve an effective sample size of 40, we need an actual sample size of 48 (Killip et al 2004). 10 patients in each of 6 clusters (GP practices) allows for 20% loss to follow up, which is realistic in general practice, where either patient or nurse may be unavailable for follow up.

For the survey, all health professionals involved with the intervention arm (n=9) and all service users in the intervention arm (n=30) will be included. The aim is to gain stakeholder views on the intervention.

For the qualitative interviews, a convenience sample of 12 participants will be selected. This will include all nurses, GP's and pharmacists in the intervention arm, as well as a purposive sample of 3 patients. The patients will be selected based on the most positive and most negative responses in the survey. The aim is to gain stakeholder views on the intervention and to supplement and illustrate the RCT data.

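### The RCT is sized for a difference between arms with GP practices randomised, but sections 7.1 and 7.5 do not name the arm contrast, the sized outcome or a method for clustering; the only named test is a within-patient McNemar test.

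*Combined protocol and SAP*

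**What the plan says.** **Design.** Section 2.2 describes "cluster group randomization by GP practice, intervention arm (ADRe Profile implementation), control arm (standard of care".

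**Sizing.** Section 7.4 starts from 17/19 (89%) improved in at least one clinical problem in an earlier single-arm study. Its figure for the comparison is an assumption: "We hypothesised that 9/19 (47%) would have shown some improvement without intervention". From these two rates the requirement is given as "necessitating an effective sample of 40 patients (20 in each arm), with 5% significance and 90% power". With ICC 0.02 and a design effect of 1.18, 40 becomes 48; six practices of 10 patients then allow for 20% loss.

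**Clustering.** Section 4.3 says "The cluster design has been accounted for in the sample size". It says nothing about the analysis.

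**Primary analysis.** Section 7.1: "Differences between before and after the intervention will be calculated for: problems addressed, prescription regimens, NHS use, and compared, adjusting for site".

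**Detailed analysis.** In section 7.5 GP practice appears beside age, diagnoses and medicines' use as factors that "will be described and accounted for in exploratory bivariate and multivariate regression analyses". The synopsis has nearly the same sentence but does not call these analyses exploratory. Both places name one test for the RCT, introduced as "using McNemar's test for related dichotomous variables", and both apply it to paired Profiles: "The prevalence of problems on the before and after profiles will be compared with two by two contingency tables".

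**Data source.** In the schedule in section 4.5, notes-based Profiles are scheduled at both RCT steps in both arms (Forms 08 and 13 in section 8.3). Self-completed and nurse- or researcher-completed Profiles are scheduled in the intervention arm only; the control arm has standard of care in those rows.

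**Endpoint.** The Phase 2 patient-count endpoint in section 2.1 counts patients whose signs and symptoms change. It goes on to refer to clinical gain and benefit, recorded in the notes and on the Profile. It does not carry the threshold of at least one problem used in 7.4.

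**The concern.** The sample size answers one question (do more patients improve with ADRe than without it?), while the only named test answers another (do patients differ before and after?). A before–after change cannot be credited to ADRe when the plan expects 47% of patients to improve without it. If McNemar's test were run on self-completed or nurse-completed Profiles, the randomised control arm would not enter the analysis at all.

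The sentences that might fill the gap leave the model open. Neither 7.1 nor 7.5 mentions arm, and the word *site* could mean practice or health board. With three practices per arm, how practice is handled affects the error rate, the power and even whether the arm effect can be estimated. Leaving that choice until the data are in hand weakens the main result of the trial.

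**Working it through.** **Inputs.** From 7.4: p1 = 17/19 = 0.895, p2 = 9/19 = 0.474, difference 0.421, 5% significance, 90% power, ICC 0.02, six practices of 10. Three practices per arm follows from the 30 intervention patients in 7.4 at 10 per practice. Eight completers per practice (48/6) assumes that the 20% loss falls evenly.

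**1. The plan's own figure.** For two independent proportions, two-sided with unpooled variance:

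n per arm = (1.960 + 1.282)² × (0.0942 + 0.2493) / 0.421² = 20.4.

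The pooled-variance formula gives 23.5 two-sided or 18.9 one-sided. At 20 per arm these three versions give power of 89.5%, 84.5% and 91.4%, so 20 per arm fits either sidedness. The design effect is 1 + (10 − 1) × 0.02 = 1.18; 40 × 1.18 = 47.2, rounded up to 48; 48/0.8 = 60. The chain reproduces as a comparison of two independent groups with a clustering allowance.

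**2. What McNemar's test compares.** It uses only the two discordant counts, patients with a problem before but not after and the reverse. Arm and practice do not enter. It can be run within each arm on the notes-based Profiles, but two within-arm tests are not a test of the difference between arms.

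**3. Adjusting for practice as a fixed effect.** With one row per patient, a model with an intercept, five practice indicators and arm has 7 columns and rank 6: practice determines arm, so the arm effect is inestimable. With before and after rows, a model with an intercept, five practice indicators, period and arm-by-period has 8 columns and rank 8, so that contrast is estimable. Whether the adjustment works depends on a model that is not stated.

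**4. Ignoring practice.** Exact enumeration with beta-binomial practice counts, a common rate of 26/38 in both arms and ICC 0.02 gives a two-sided chi-square type I error of 6.9% (8 per practice) or 7.0% (10). At ICC 0 the same test has 5.2% and 4.8%.

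**5. Practice-level t-test, 3 v 3 practices, 4 df, ICC 0.02.** SE = √[DE × (0.0942 + 0.2493) / (3m)], with m completers per practice and DE = 1 + (m − 1) × 0.02.

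- m = 8: DE = 1.14, SE = √(1.14 × 0.3435/24) = 0.128, noncentrality 0.421/0.128 = 3.30.
- m = 10: DE = 1.18, SE = √(1.18 × 0.3435/30) = 0.116, noncentrality 3.62.

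| Completers per practice | Two-sided power: enumeration / noncentral t | One-sided power: enumeration / noncentral t |
|---|---|---|
| 8 | 66.7% / 69.7% | 83.3% / 85.2% |
| 10 | 74.2% / 77.2% | 88.6% / 90.3% |

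Its two-sided type I error is 4.6% in both cases. The expected 95% CI half-width is about 33 percentage points (8) or 30 (10).

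**6. Where the lost power goes.** At ICC 0 with 8 per practice, enumeration still gives only 72% two-sided, so most of the loss comes from the 4 df. A chi-square divided by the design effect at ICC 0.02 gives 88.5% power and 5.4% type I error with 8, and about 93% and 5.2% with 10. If the true ICC were 0.05 (an assumption) while the correction still used 0.02, its type I error would be about 8%.

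**The case against.** The strongest reply is that the comparison is there, if tersely put. In a parallel-arm trial, the word *compared* in 7.1 most naturally means between arms. The synopsis describes the trial as multiple-site and lists GP practices or community clinics as the study centres, so *site* probably means practice. McNemar's test is nowhere called primary. This stands in part: a reader might infer that the plan contains no between-arm comparison at all, and the documents do not support that. The gap that remains is that the contrast, the sized outcome and the clustering method are not named.

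A reader might also infer that the section 2.1 endpoint has no direction or data source. Its second sentence supplies both: benefit, and the notes and Profile. What is missing is the threshold of at least one problem, and which of the two sources governs, given that only the notes-based Profiles are scheduled in both arms.

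It may further be said that several objectives are exploratory and that the inflation to about 7% is modest. Both are true. But 7.1 is headed as the primary efficacy analysis and 7.4 claims 90% power, so a specified test is a fair expectation. The main fault is the unnamed randomised contrast rather than the size of the inflation.

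**Conclusion.** The concern holds in this form: the plan mentions a comparison and an adjustment, but it does not specify the between-arm analysis for which the trial was sized, and its one named RCT test cannot supply it. Followed as written, the text could credit ADRe with change that the plan itself expects in 47% of patients without it.

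The size depends on the method eventually used: type I error of about 7% rather than 5% if practice is ignored; no estimable arm effect with fixed practice effects and one row per patient; or two-sided power of 67–70% (8 completers) or 74–77% (10) with a practice-level t-test.

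A reader might infer that the trial is simply underpowered at 67%. The documents do not support that, because they name no test: the figure belongs to the 4-df t-test, and a design-effect-corrected chi-square would give about 88% two-sided with 8 completers, provided the true ICC is 0.02. Nor is the unstated sidedness an error, since 20 per arm fits either; it needs clarifying.

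The figures assume three practices per arm, equal numbers of completers, ICC 0.02 unless stated, and 89% v 47% for the outcome actually analysed.

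**What to change.** **In 7.1, 7.5 and the synopsis**
- Name one primary analysis: the intervention v control difference in the proportion of patients with at least one problem improved, measured from a source available in both arms. As scheduled, that is the notes-based Profiles.
- Use a method that respects the six practices and has small-sample inference, for example a t-test on the six practice proportions (4 df) or a mixed model with a random practice effect and small-sample degrees of freedom.
- Say that *site* means practice.
- Keep McNemar's test as a descriptive within-arm summary.

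**In 2.1**
- Add the threshold of at least one problem to the patient-count endpoint, and state how newly identified problems count. That rule is for the sponsor to set.

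**In 7.4**
- State the sidedness and the power for the test chosen. For the practice-level t-test this is about 67–70% two-sided (83–85% one-sided) with 8 completers per practice, and 74–77% (89–90%) with 10. A mixed model needs its own calculation.
- Alternatively, present the RCT as estimating the effect with a confidence interval, with an expected half-width of about 30–33 percentage points on the practice-level analysis.

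**Cost.** Wording only; Forms 08 and 13 already provide for the data. There are two downsides. The stated power becomes less favourable under the t-test. And a notes-based outcome depends on what is recorded, which ADRe may itself change; the 89% came from a study using ADRe Profiles, so 89% v 47% may not carry over, and any restated power is conditional on it.

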1.3 Clinical Data

Medication monitoring and monitoring patients for potential adverse drug reactions has been described as an 'orphan task' in the past due to its position on the interprofessional boundary between pharmacy, medicine and nursing and the subsequent deficiency in ownership (Jordan, 2002, Jordan et al., 2016). Recent studies confirm the lack of clarity of the nurses' roles in medication management (De Baetselier et al., 2019) and effective teamwork has been affirmed as a facilitator of safe management of polypharmacy (WHO, 2019), and medication management overall (WHO, 2017). ADRe Profile is an instrument that involves nurses, pharmacists, prescribers and patients in monitoring for adverse drug reactions to medicines. Nurses and patients identify the problems and may solve some of them, pharmacists review the medicines and prescribers may be provided with recommendations to consider adjustment of the prescriptions.

To date, two randomised controlled trials and five observational/before and after studies have investigated the clinical impact of the ADRe Profile. In total, 168 study participants had the ADRe Profile implemented. Majority of the participants were prescribed mental health medicines (antipsychotics, antidepressants or anti-epileptics), one study included patients with respiratory diseases, taking bronchodilators, corticosteroids or leukotriene receptor antagonists. The setting was mostly in the community, with 3 nursing homes, 3 community mental health settings and one outpatient respiratory clinic.

In two of the community mental health settings, the mean number of problems actioned increased from 0.35 with no ADRe Profile to 3 with ADRe Profile (Jordan et al., 2002; Jordan, 2002). Little change in the number of problems actioned was noted in the comparator groups. The mean number of problems detected increased from 2 without the Profile to 9 with the Profile in one of the studies (Jordan, 2002), no information was offered in the other study. Most actions taken were to alleviate physical health problems.

Another study from an acute mental health service setting identified and addressed health problems for all participants (the mean increase of actions taken was 11.9, SD = 4.7, range 2-20) (Jones et al., 2016). Some of the problems identified were orthostatic hypotension, hypertension, constipation or inadequate diet, two of the

SU Non CTIMP Healthcare Research Protocol

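### Run problem by problem in its exact or continuity-corrected form, the one named RCT test (McNemar) cannot show the removal of a problem present in five or fewer intervention patients, and the number of problems present per patient has no test

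*Combined protocol and SAP*

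**What the plan says.** Section 7.5, under Randomised Controlled Trial, states that "The prevalence of problems on the before and after profiles will be compared with two by two contingency tables". The method it gives for this is "using McNemar's test for related dichotomous variables". The synopsis repeats this. No other hypothesis test is named for the RCT.

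Two other parts of the plan bear on the point:

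- Section 7.1 will compare before and after values of problems addressed, prescription regimens and NHS use, adjusting for site. Section 7.5 adds the number and nature of problems addressed, with exploratory regressions. Neither section names a test or a model.
- The sample size in section 7.4 concerns a different quantity, the proportion of patients in each arm who improve in at least one problem, "with 5% significance and 90% power".

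The plan does not say which version of McNemar's test is meant, whether it is one- or two-sided, in which arm it is run, whether there is one table per problem, or how many tests there will be.

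**The concern.** McNemar's test uses only the patients whose status changes. In an arm of 24 to 30 patients, many individual problems may be present in only a handful, and the test then has too few changes to reach 5% whatever the intervention does. The opposite risk comes from running many such tests at an unadjusted 5%, where a few items can be significant by chance. Section 2.1 makes the number and nature of problems a primary Phase 2 endpoint, so the one named test would give a fragmented and possibly misleading answer on it.

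**Working it through.** **Number of pairs.** First, the plan's own sample size. Inputs from section 7.4: "17/19 (89%) had improvement in at least 1 clinical problem" with the Profile; "We hypothesised that 9/19 (47%) would have shown some improvement without intervention"; 5% significance (two-sided assumed); 90% power; ICC 0.02; "a design effect of 1.18".

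- Per arm, unpooled variance: (1.960 + 1.282)² × [0.895×0.105 + 0.474×0.526] / (0.421)² = 20.4, against the stated 20. The pooled-variance formula gives 24.
- Design effect: 1 + (10 − 1)×0.02 = 1.18. Then 40 × 1.18 = 47.2, taken as 48, and 48/0.8 = 60.
- So there are 30 patients per arm (section 3 also gives 30 for the intervention arm), and 30 × 0.8 = 24 after loss.

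**Smallest result that can be significant.** With b changes one way and none the other: exact two-sided p = 2 × 0.5^b; mid-p = 0.5^b; continuity-corrected chi-square = (b − 1)²/b; uncorrected chi-square = b.

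| b | Exact | Continuity-corrected | Mid-p | Uncorrected |
|---|---|---|---|---|
| 3 | 0.25 | 0.248 | 0.125 | 0.083 |
| 4 | 0.125 | 0.134 | 0.0625 | 0.0455 |
| 5 | 0.0625 | 0.074 | 0.031 | 0.025 |
| 6 | 0.031 | 0.041 | 0.016 | 0.014 |

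The minimum is six (exact or continuity-corrected), five (mid-p) or four (uncorrected). Five patients are 5/24 = 21% or 5/30 = 17%. One new case raises the exact requirement to 8 against 1 (p = 0.039).

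**Chance of reaching six if the problem is wholly removed** (binomial probability of at least six affected at baseline, no new cases):

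| True prevalence | 24 pairs | 30 pairs |
|---|---|---|
| 10% | 3% | 7% |
| 20% | 34% | 57% |
| 30% | 77% | 92% |

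**Illustration against a count per patient.** The documents give no item count or prevalence for this population, so these inputs are assumptions: 40 items and nine problems per patient (prevalence 9/40 = 22.5%), 40% of problems resolve, and new problems arise in 5% of unaffected patient-items. The nine is borrowed from section 1.3: "The mean number of problems detected increased from 2 without the Profile to 9 with the Profile in one of the studies".

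- Per item: resolving 0.225×0.40 = 0.090; new 0.775×0.05 = 0.03875; discordant 0.12875. Exact McNemar power is about 1% (24 pairs) and 2% (30). The uncorrected version gives 7% and 10%.
- Count per patient, items independent: mean fall 40×(0.090 − 0.03875) = 2.05; variance 40×(0.12875 − 0.05125²) = 5.04, SD 2.25. The standardised change is 0.913, and 0.913×√24 = 4.47, so a paired t-test has about 99% power.
- Count per patient, with beta-binomial within-patient correlation in presence, resolution and onset (simulation): about 66% and 74% at correlation 0.1, and about 44-45% and 52-53% at 0.2.

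**Chance hits with no true change, 40 independent items.** With 12.9% of pairs discordant (as above), the uncorrected test rejects 3.2% of the time on 24 pairs and 4.2% on 30, so 40 × 0.032 = 1.3 and 40 × 0.042 = 1.7. With 18% discordant (0.090 each way) the figures are 1.8 and 1.9. Mid-p gives 0.4 to 1.1, and exact tests fewer than 0.5.

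**The case against.** The strongest reply is that these tables are exploratory description of which problems changed, and that the plan compares the number of problems elsewhere. A reader might infer that the plan ignores the number of problems altogether. Sections 7.1 and 7.5 do not support that, because a comparison of problems addressed is planned. What remains is that problems addressed are not problems present, and that no test or model is attached to either.

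Testing problem by problem, and 24 to 30 pairs, are both inferences. If both arms were pooled (48 to 60 pairs), six patients would be 12.5% to 10%; but pooling would mix the randomised arms. If the sentence means a single table for any problem, patients with several problems each would mostly be positive both times, leaving few changes to test.

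A reader might also infer that almost every problem will come out non-significant. The documents give no prevalences, so this cannot be claimed. A problem in 30% of patients has a 77% to 92% chance of significance if wholly removed. At 50% prevalence with 40% resolving and 5% new, exact power is 23% (24 pairs) or 37% (30).

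Finally, the 99% figure for the count needs items to be independent within patients, which is doubtful for symptoms in multimorbid older people. That objection stands, and the gain should be shown only as a range.

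**Conclusion.** The point holds as a limit on the one named test. Under the exact or continuity-corrected two-sided version, on the per-problem reading and in the intervention arm, the removal of a problem present in five or fewer patients cannot be shown at 5%. The limit falls to four or fewer with mid-p and three or fewer with the uncorrected test, so it shifts without disappearing. Multiplicity control would raise it: Bonferroni over 20 items (an assumed number) would need ten one-way changes.

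The advantage of a per-patient count is real in the example but uncertain in size: about 44% to 99% power against 1-2% per item, depending on assumed item number, prevalence, change rates and within-patient correlation.

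A reader might take this as showing that 60 patients is too few. It does not: section 7.4 sizes the trial on a between-arm proportion, and that calculation is not challenged here.

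**What to change.** Replace item-by-item significance testing in section 7.5 and the synopsis with one patient-level analysis of the number of problems per patient:

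- **Between arms:** follow-up count adjusted for baseline count, with arm in the model and allowance for clustering by practice. Use the notes-derived profile at both times, since section 4.5 collects it in both arms and gives control patients no other. With six practices, name a method suited to few clusters.
- **Within the intervention arm:** the before and after count from nurse- or researcher-completed profiles, as supportive evidence only, because it has no concurrent control.
- **Interpretation:** say in advance how a rise in count will be read, because the Profile itself increases detection (section 1.3).
- **Individual problems:** before and after counts with a 95% confidence interval for the paired difference and no p-value. If p-values are kept, state the McNemar version and arm and control the false discovery rate.
- **Power:** if a figure is quoted for the count, give a range over stated assumptions.

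The cost is a change of wording. The data are already on the planned forms (section 8.3). What is given up is unadjusted item-level p-values.
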